2.2 Efficacy evaluation

The Full Analysis Set (FAS) is the primary analysis population for efficacy analyses, following the intention-to-treat principle. Per-protocol (PPS) population will be used in the supportive analysis for primary and key secondary efficacy parameters (Table 2-5).

Table 2-5 List of efficacy endpoints and analyses

Endpoint	Analysis set	Analysis method
Primary efficacy endpoint ($\alpha=0.025$, 1-sided)		
1 Trichotomous composite (success, failure, no change)	FAS/PPS	Ordered logistic-regression (proportional odds) model that includes treatment and [REDACTED] as factors (primary analysis is on FAS)
	FAS	Ordered logistic-regression model including treatment only (sensitivity analysis 1)
	FAS	van Elteren extension of the Wilcoxon test stratified by [REDACTED] (sensitivity analysis 2)
Secondary efficacy endpoints (if primary endpoint is significant, then test in the order listed below at $\alpha=0.05$ each)		
1 Time (hours) to WHF through Day 5	FAS/PPS	Gehan's generalized Wilcoxon test
2 Time (days) to CV death through Day 180	FAS/PPS	Kaplan-Meier estimates and log-rank test
3 Time (days) to all-cause death through Day 180.	FAS	Kaplan-Meier estimates and log-rank test
Other efficacy endpoints (at $\alpha=0.05$, no multiplicity adjustment)		
1 Time (hours) to moderate or marked improvements in dyspnea by Likert scale through Day 5	FAS	Wilcoxon rank-sum test
2 Dyspnea by VAS-AUC changes (from baseline) through Day 5	FAS	ANCOVA
3 Length of stay (# of days) in index ICU/CCU	FAS	Wilcoxon rank-sum test
4 Renal dysfunction or worsening of renal function through Day 5	FAS	chi-squared test
5 Time (days) to re-hospitalization due to HF and renal failure through Day 180	FAS	Kaplan-Meier estimates and log rank test
6 Time (days) to CV death or re-hospitalization due to HF/RF through Day 180	FAS	Kaplan-Meier estimates and log rank test
7 Time to in-hospital worsening heart failure through Day 5 defined by symptoms and signs		Kaplan-Meier estimates and log rank test
8 Use of loop diuretics and vasoactive agents through Day 5	FAS	chi-squared test
9 Changes in cardio-renal biomarkers (Day 2 and Day 5)	FAS	Summary statistics, see Section 2.2.3

2.2.1 Primary efficacy variable and analyses

[figure not shown]
2.2.1.1 Primary efficacy variable

The primary efficacy variable is the trichotomous clinical composite endpoint based on

- (i) treatment 'success': as of congestion improvement of dyspnea in Likert (moderately and markedly improvement) AND at least 2 points improvement for at least 2 out of 4 signs and symptoms variables (orthopnea, edema, rales and JVP) at Day 2
- (ii) treatment 'failure': as of in-hospital worsening heart failure (WHF), all causes of death, or re-hospitalization due to heart failure (HF) or renal failure (RF) through Day 5
- (iii) no change: neither of (i) or (ii)

[figure not shown]
If a patient meets (i) and (ii), he will only be counted as 'failure' (ii).

For missing Day 2 Likert or signs and symptoms, the previous available post baseline values will be used.

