	

• Treatment success is defined as moderate or marked improvement in patient reported dyspnea by Likert scale AND at least 2 points improvement for at least 2 out of 4 physician assessed signs and symptoms including orthopnea, rales, edema and jugular venous pulse (JVP) and none of them deteriorating (<math>\geq</math> 0 point improvement) at Day 2. Refer to the efficacy assessment 1 Section 6.4.1 and the physician assessment of signs and symptoms Section 15 Appendix 3.

• Treatment failure is defined as in-hospital worsening heart failure or re-hospitalization due to heart failure or renal failure (RF) or death through Day 5.

• All remaining patients are classified as having unchanged treatment status if they meet neither the criteria for treatment success at Day 2 nor the criteria for treatment failure through Day 5.

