Efficacy assessments	
Primary efficacy assessment
 
The primary efficacy variable is defined as the clinical composite endpoint based on:
 

• Treatment success defined as

• Moderate /marked improvement in dyspnea by the Likert Scale at Day 2 AND <math>\geq 2</math> points improvement in <math>\geq 2</math> of 4 physician assessed symptoms and signs of congestion (orthopnea, edema, rales and JVP) and none of them deteriorating (<math>\geq 0</math> point improvement) at Day 2 Refer to the physician assessment of signs and symptoms, Section 15 Appendix 3.

• Treatment failure defined as

• In-hospital worsening heart failure through Day 5 or

• All-causes of death through Day 5, or re-hospitalization due to heart failure or renal failure through Day 5

• Unchanged defined as

• All remaining patients are classified as having unchanged treatment status if they meet neither the criteria for treatment success at Day 2 nor the criteria for treatment failure through Day 5.

 
If a patient is determined as treatment failure through Day 5, then he/she will be excluded from the assessment of treatment success at Day 2 or unchanged even if the patient experience improved signs and symptoms at Day 2.
 
Secondary assessments
 

• Time to WHF through Day 5

• Time to cardiovascular death during a follow-up period of 180 days

• Time to all-cause death through a follow-up period of 180 days

 
Other secondary efficacy assessments:
 

• Time to moderate or marked improvements in dyspnea by Likert scale through Day 5

• Dyspnea by VAS-AUC changes through Day 5

• Length of stay in index ICU/CCU

• Renal dysfunction & prevention of in-hospital worsening of renal function through Day 5

• Time to re-hospitalization due to HF and renal impairment through Day 180

• Time to CV death or re-hospitalization due to HF/RF through Day 180

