Data analysis	
The primary efficacy variable will be the trichotomous clinical composite endpoint based on (i) treatment 'success' of congestion improvement of dyspnea in Likert (moderately and markedly improvement) AND at least 2 points improvement for at least 2 out of 4 signs and symptoms variables at Day 2, (ii) treatment 'failure' of in-hospital worsening heart failure, death or re-hospitalization due to HF or RF through Day 5 and (iii) neither as 'no change'.
 
The primary analysis will be the comparison of two trinomial distributions of trichotomous clinical composite endpoint between placebo and serelaxin groups.
 
The primary statistical hypothesis is:
 
<math>H_0: \theta \geq 1</math> vs <math>H_a: \theta < 1</math>
 
Where <math>\theta</math> is the common value of two odds ratios of clinical composite endpoint ('failure' versus combined 'no change' and 'success' or combined 'failure' and 'no change' versus 'success') between placebo and serelaxin. <math>H_0</math> is the null hypothesis and <math>H_a</math> is the alternative hypothesis (Whitehead 1993). The hypothesis will be tested based on the FAS with an ordered logistic-regression (proportional odds) model that includes treatment and country as factors (McCullagh, 1980). Given the classification of (-1 denoting 'failure', 0 for 'no change' and 1 for 'success', an odds ratio of less than 1 would favor serelaxin. The odds ratio and 95% confidence interval for the treatment effect will be calculated and presented. There are three secondary variables:
 

• WHF through Day 5

• CV death through Day 180

• All-cause death through Day 180.

 
All of these secondary variables are time-to-event variables. The hypothesis will be tested based on the FAS at a significance level of 0.025 (one-sided).
 
The three secondary variables will be tested using hierarchical testing procedure in controlling overall <math>\alpha</math> of 0.05 (Bretz, et al 2009). If primary endpoint is significant, WHF will be tested first at <math>\alpha</math> of 0.05. If WHF is significant at the same <math>\alpha</math> level then will proceed to test CV death and only

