## **2 Study objectives**

### **2.1 Primary objective(s)**

- To demonstrate that serelaxin is superior to placebo in improving the clinical composite of “treatment success,” “treatment failure” and “unchanged”
  - Treatment success is defined as moderate or marked improvement in patient reported dyspnea by Likert scale AND  $\geq 2$  points improvement for at least 2 out of 4 physician assessed signs and symptoms including orthopnea, rales, edema and JVP and none of them deteriorating ( $\geq 0$  point improvement) at Day 2.  
Refer to the Efficacy assessment 1 [Section 6.4.1](#) and the physician assessment of signs and symptoms [Section 15 Appendix 3](#).
  - Treatment failure is defined as in-hospital worsening of heart failure or re-hospitalization due to HF or RF or death through Day 5.

- All remaining patients are classified as having unchanged treatment status if they meet neither the criteria for treatment success at Day 2 nor the criteria for treatment failure through Day 5.

Worsening heart failure (WHF) is defined as in-hospital worsening signs and/or symptoms of heart failure that require an intensification of intravenous therapy for heart failure or mechanical ventilator, renal or circulatory support. Such treatment can include the institution or up-titration of IV furosemide, IV nitrates or any other IV medication for heart failure, or institution of mechanical support such as mechanical ventilation, ultrafiltration, hemodialysis, intra-aortic balloon pump or ventricular assist device.

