Therefore, it is incomplete to evaluate the disease status of AHF by assessing a single clinical symptom. In this study the treatment success at Day 2 is defined by both the moderate or marked improvement in patient reported dyspnea and 2 or more points of improvement in at least 2 out of 4 physician assessed signs of congestion and none of them deteriorating ( $\geq 0$  point improvement). Thus, treatment success requires both relief of patient-reported dyspnea and improvement in physician-assessed signs and symptoms of congestion. This requirement of significant early improvement in multiple signs and symptoms of congestion for treatment success is stringent in recognizing that standard care is generally effective in improving some of the symptoms, e.g. dyspnea. Therefore, a clinical composite endpoint with treatment success as one of the components that is comprised of multiple signs and symptoms of congestion could reflect more holistically the status of congestion and a more clinically reliable indicator for therapeutic efficacy in clinical trials. In summary, the treatment success definition reflects the goals of acute heart failure treatment (ie, relief of dyspnea AND congestion) and represents a comprehensive assessment of the treatment effect.

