#### **6.4.3 Appropriateness of efficacy assessments**

The primary efficacy endpoint is defined as the clinical composite comprised of treatment success at Day 2 or treatment failure or unchanged through Day 5. Treatment success is assessed by moderate/ marked improvement in dyspnea measured by Likert Scale at Day 2 AND a minimum of 2 points improvement in at least 2 out of 4 physician assessed symptoms and signs of congestion (orthopnea, edema, rales and JVP) and none of them deteriorating ( $\geq 0$  point improvement) at Day 2 as compared to baseline. The treatment failure is defined as in-hospital WHF, death, or re-hospitalization through Day 5. To define the treatment success by

improvement in signs and symptoms at Day 2 is to evaluate the early therapeutic effect of serelaxin for the relief of congestion; to define the treatment failure as WHF, death and re-hospitalization through Day 5 is to assess the therapeutic effect is sustained by preventing these in-hospital worsening HF events. If a patient is determined as treatment failure, he/she will be excluded from the assessment of treatment success or unchanged even if the patient experienced improved signs and symptoms at Day 2.

By applying this clinical composite endpoint definition to the data of the completed RELAX-AHF study, the post-hoc analysis showed that the patients who met the definition of “treatment failure” comprised 11.9% in placebo group and 6.4% in the serelaxin group, and the relative risk reduction (RRR) in favor of serelaxin was 45%. The patients who met the definition of “treatment success” comprised 26.0% in placebo group and 31.7% in the serelaxin group (the relative increase in the proportion of “treatment success” was 22%). Using the analysis of maximum likelihood estimates, the serelaxin treatment showed statistically significant benefits in the clinical composite endpoint compared to placebo ( $p < 0.001$ ).

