#### **9.4.1 Variable(s)**

The primary efficacy variable will be the trichotomous clinical composite endpoint based on (i) treatment ‘success’ of congestion improvement of dyspnea in Likert (moderately and markedly improvement) and at least 2 points improvement for at least 2 out of 4 signs and symptoms variables at Day 2, (ii) treatment ‘failure’ of in-hospital worsening heart failure, death or re-hospitalization due to HF or RF through Day 5 and (iii) neither as ‘no change’.

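### The SAP and the protocol's analysis text define treatment success without the no-deterioration condition that the primary objective requires.

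*SAP*

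**What the plan says.** **With the condition.** The primary objective in protocol 2.1 asks for improvement in "physician assessed signs and symptoms including orthopnea, rales, edema and JVP and none of them deteriorating". The synopsis repeats this under the primary objective ("physician assessed signs and symptoms including orthopnea, rales, edema and jugular venous pulse (JVP) and none of them deteriorating") and under efficacy assessments ("physician assessed symptoms and signs of congestion (orthopnea, edema, rales and JVP) and none of them deteriorating"). Protocol 3.2 has "2 or more points of improvement in at least 2 out of 4 physician assessed signs of congestion and none of them deteriorating", and 6.4.1 and 6.4.3 carry the same requirement. These passages define not deteriorating as a change of at least 0 points.

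**Without it.** The synopsis data analysis has "AND at least 2 points improvement for at least 2 out of 4 signs and symptoms variables at Day 2", and protocol 9.4.1 has "and at least 2 points improvement for at least 2 out of 4 signs and symptoms variables at Day 2". SAP 2.2.1.1 has "at least 2 points improvement for at least 2 out of 4 signs and symptoms variables (orthopnea, edema, rales and JVP) at Day 2" and then closes the rule: anyone who is neither a success nor a failure is no change. SAP section 2 refers the analyst to protocol section 9, whose visible text does not restore the condition. The missing-data rules (protocol 9.4.3, SAP 2.2.1.3) do not restore it either.

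**The concern.** The composite is the only primary endpoint and the gate to all three secondary tests. Two analysts working from different sections would build different primary datasets, and a choice between them after unblinding could be challenged as data-driven. The visible sensitivity analyses in SAP Table 2-5 change the model or the analysis set but never the success definition, so none would show the difference.

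The benchmarks are also affected. Protocol 6.4.3 states the definition with the condition and then reports rates obtained "By applying this clinical composite endpoint definition to the data of the completed RELAX-AHF study". Protocol 9.7 plans to compare blinded pooled success and failure rates with RELAX-AHF at about 70% enrolment (0.70 × 1,520 = 1,064 patients). If the pooled rates follow the SAP rule, success is counted more loosely than in its benchmark.

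**Working it through.** **1. Can the two rules classify a patient differently?** The Appendix 3 scales allow it. Suppose orthopnea goes from 3 to 1, rales from the highest grade to the second lowest (two grades), and edema from 0 to 1+. JVP is unchanged, dyspnea is markedly better, and there is no failure event through Day 5.

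- Protocol 2.1: edema has worsened, so the patient is unchanged.
- SAP 2.2.1.1: two of four signs improved by two points, so the patient is a success.

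Failure overrides success under both rules, so failures are untouched. The only possible movement is from unchanged to success.

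**2. The plan's sample size.** Inputs are placebo failure 11.9% and success 26.0% (protocol 6.4.3), hence unchanged 100 − 11.9 − 26.0 = 62.1%. The common odds ratio is 0.75, with two-sided 5%, 80% power and 1:1 allocation (protocol 9.7). That these rates are the planning rates is an inference: SAP 2.7 says only that the placebo distribution came from RELAX-AHF.

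- Serelaxin failure: odds 0.119/0.881 × 0.75 = 0.1013, giving 9.2%.
- Serelaxin non-success: odds 0.74/0.26 × 0.75 = 2.1346, giving 68.1%. Success is therefore 31.9% and unchanged 58.9%.
- Mean proportions: 0.1055, 0.6050, 0.2895. One minus the sum of their cubes is 0.7531.
- Whitehead: N = 12 × (1.960 + 0.842)² / (0.2877² × 0.7531) = 1,511, against 1,520 stated (0.6% apart).

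The figure reproduces, which supports the inference that planning used the definition with the condition.

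**3. Size of the effect.** The documents do not say how often a success also has a worsened sign, so the movement is assumed. Power is from a proportional-odds model fitted to expected counts at 760 per arm, with a two-sided Wald test at 0.05. With no movement it gives 79.9% (the Whitehead formula gives 80.2% at 1,520).

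| Moved from unchanged to success | Patients, if equal in both arms | Odds ratio and power, equal movement | Power if the odds ratio stays 0.75 |
|---|---|---|---|
| 0% | 0 | 0.750, 79.9% | 79.9% |
| 1% | 15 | 0.753, 79.2% | 80.4% |
| 3% | 46 | 0.759, 77.8% | 81.2% |
| 5% | 76 | 0.764, 76.5% | 81.8% |

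Even the direction of the power change depends on the assumption. At 5%, the placebo success rate becomes 31%, so 5/31 = 16% of placebo successes would carry a worsened sign.

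**4. Blinded pooled success rate.** Here the direction is certain: the looser rule cannot lower it. With equal movement of 1%, 3% or 5% it rises from 29.0% to 30.0%, 32.0% or 34.0%. The Whitehead N computed from the pooled rates at an odds ratio of 0.75 falls from 1,511 to 1,495, 1,466 or 1,443.

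**The case against.** **Hidden text.** Protocol 9.4.2 and 9.4.4 and SAP 2.2.1.2 are not in the public text, and a figure is missing inside SAP 2.2.1.1. The condition, or an analysis varying it, may be stated there. This stands as a limit on what can be known of the programming and of the sensitivity analyses. It does not remove the conflict between the visible definitions.

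**Shorthand.** The three passages use similar compressed wording, and nothing suggests a deliberate change of endpoint; this may be a transcription omission. That is plausible, but SAP 2.2.1.1 names the four signs and closes the classification. A programmer who follows it would not apply the condition.

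**No demonstrated effect.** The frequency is unknown, the 1% to 5% movements are assumed, and the power changes are small. This is correct, and the severity does not rest on them.

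**Re-estimation.** Protocol 9.7 provides only for an increase, and only if the rates are much lower than expected. A slightly inflated success rate would matter only if it masked a real shortfall, and nothing visible says the blinded rates follow the SAP rule. The point is therefore conditional and secondary.

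**The remedy.** In the extracted text, protocol 6.4.1 also lists in-hospital worsening heart failure under success, possibly an editing or extraction artefact. It does no harm if the added words are written out in full. A sign with a missing baseline is set to zero change and so would pass the restored condition automatically. This is consistent with the at-least-0 wording.

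**Conclusion.** The concern holds and must be fixed before unblinding. Six places in the protocol require that no sign deteriorates. The synopsis data analysis, protocol 9.4.1 and SAP 2.2.1.1 do not. Followed as written, the SAP can count as successes patients whom the primary objective calls unchanged, and never the reverse.

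Confidence that the visible definitions conflict is high. The number of patients affected and the direction of any effect on the odds ratio are unknown. The power range above rests on assumed movement and on the inferred planning rates. Neither the planned 1,520 nor the type I error is in question.

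**What to change.** 1. Before unblinding, add to item (i) of SAP 2.2.1.1 that none of the four signs and symptoms deteriorates at Day 2 (change of at least 0 points). Cite protocol 2.1 and 6.4.1 as the governing definition, and program the condition.
2. Use the same derivation for the blinded pooled rates in protocol 9.7.
3. Align protocol 9.4.1 and the synopsis data analysis at the next amendment.
4. Leave the missing-baseline rule as it is. A sentence saying that a change set to 0 meets the condition would remove doubt.

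The cost is one SAP clause and one programming condition, with no new data and no change to the planned sample size. The protocol edits need a written amendment with the approvals in protocol 11.1. They can wait, because the SAP clause settles the derivation.

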2.2.1.3 Handling of missing values/censoring/discontinuations

The components of trichotomous clinical composite endpoint are all categorical variables. Missing categorical value will be replaced with the last preceding non-missing value. These will include dyspnea Likert scale at Day 2, four signs and symptoms at Day 2 and worsening heart failure through Day 5. In the evaluation of treatment success for the four signs and symptoms, the change from baseline will need to be calculated. If there is a missing baseline value, say a subject with missing JVP at baseline, this subject's change of JVP at Day 2 will be set as 0-point improvement, i.e., will not be contributed as 2-point improvement for JVP.

2.2.2 Secondary efficacy variables and analyses

There are three secondary variables:

- WHF through Day 5
- CV death through Day 180
- All-cause death through Day 180

All of these secondary variables are time-to-event variables. The hypothesis will be tested based on the FAS at a significance level of 0.025 (one-sided).

The three secondary variables will be tested using hierarchical testing procedure in controlling overall α of 0.05 (Bretz et al 2009). If primary endpoint is significant, WHF will be tested first at α of 0.05. If WHF is significant at the same α level then will proceed to test CV death and only if CV death is significant then will test all-cause death at α of 0.05.

WHF through Day 5

Time to WHF through Day 5 will be analyzed using Gehan's generalized Wilcoxon test. Subjects died in the 5-day period will be considered as having WHF event. Event date and time will be used at calculating the time to event for better precision, and convert it back to days.

Time-to-event (days) = (first event date/time – baseline date/time),

For those subjects without events, the censoring date will be the earlier of

- Hour 120 (5 days)
- The last date at which the vital status was known, including last visit or contact

Kaplan-Meier curves will be presented graphically by treatment group and Kaplan-Meier estimates for selected time points with 95% confidence intervals will be tabulated.

In addition, analyses will be performed using a modified definition of WHF, e.g. subjects with (1) worsening signs AND symptoms or (2) IV intervention and/or mechanical support. Another sensitivity analyses that exclude subjects whose only symptom is abdominal bloating/discomfort or fatigue/decreased exercise tolerance will also be provided.

CV death through Day 180

CV death will be analyzed with a log-rank test. The time-to-event will be calculated days by subtracting the randomization date from the event date. Number and percentage of subjects who died from cardiovascular reasons based on the number of subjects in the population as denominator will be provided by treatment group. The hazard ratio (relative risk) and its associated two-sided 95% confidence interval will be estimated based on a Cox proportional hazards model with treatment assignment as a factor.

In addition, the Kaplan-Meier estimates of the survival functions for each treatment group will be plotted. The Kaplan-Meier estimates of the cumulative event rate will also be presented in tables by treatment group for each day and also by time interval.

For CV death, a patient without an event will be censored at the earlier of:

- Date of death for non-CV related causes
- The last date at which the vital status was known, including last visit or contact
- Day 180

An adjudicated death with unknown cause will be classified as a CV death. Similarly, investigator suspected deaths of unknown cause will be classified as CV deaths.

All-cause death through Day 180

All-cause death through Day 180 will be analyzed similarly to CV death through Day 180. A patient without an event will be censored at the last date at which the vital status was known (including last visit or contact) or at Day 180.

Of note, CV death and all-cause death will be two efficacy variables for bridging with other global studies.

